**ABSTRACT:**

Children with neurofibromatosis type 1 (NF1) commonly suffer from the effects of cognitive, behavioral, and motor impairments. At present, there is no specific treatment for this NF1 complication. ***In this project, we will assess the safety and clinical benefit of N-acetylcysteine (NAC) as a pharmacological intervention in children with NF1.*** This drug choice is based on the recent findings from mouse models to study the central nervous system manifestations of NF1 at Cincinnati Children's Hospital Medical Center (CCHMC). These findings revealed a role for myelin-forming oligodendrocytes in the control of nitric oxide synthases (NOS) and their product, nitric oxide (NO), in maintenance of brain structure and function, including regulation of behavior and motor control. Treating these mice with NAC corrected cellular and behavioral abnormalities. This data from animal models of NF1 along with uncontrolled clinical observations in children with NF1 suggest that the antioxidant compound, NAC, may reduce these impairments. Therefore, we propose performing a single center double-blind placebo controlled, prospective, Phase II study to explore safety, tolerability, and efficacy of NAC on motor behavior and/or learning in children with NF1 aged 8 through 16 years old. Participants will be carefully monitored for side effects. Primary and secondary outcome measures will be administered at baseline, follow-up, and post-treatment.

**PURPOSE OF STUDY:**

This is a phase II clinical trial with the goal to explore safety, tolerability, and efficacy of NAC on motor behavior in children with NF1 aged 8 through 16 years old. *We hypothesize that NAC therapy will improve motor function evaluated by the PANESS scale. This is based on studies demonstrating that NAC significantly improved impairments in the animal model of NF1. We will also analyze NAC effects on attention deficit and impulsivity in children with NF1.*

This study will also help develop novel predictive biomarkers of response to neurocognitive therapies in patients with NF1 which are needed to evaluate treatment outcomes.

We will gain information in children with NF1 about possible clinical benefit of anti-oxidant treatment and to develop and evaluate quantitative brain-based and blood biomarkers relating to presence of NF1, symptom severity, and response to antioxidant therapy. Clinically, 50% of children with NF1 are underperforming or failing at school [1]. This frequently leads to decreased educational attainment and fewer opportunities as adults. An important first step was our preliminary work using the PANESS scale and Transcranial Magnetic Stimulation (TMS)-evoked Short Interval Cortical Inhibition (rSICI) in children with NF1. We propose to develop and extend our understanding of NF1-related motor and learning behavior in response to antioxidant therapy with NAC. The purpose of the present study is to 1) evaluate tolerability, safety, and clinical benefit of NAC in this double-blind placebo controlled study using the motor function scale (PANESS); 2) to evaluate the effects of NAC on measures of NF1 neurocognitive symptomatology (ADHD/impulsive symptoms, executive function, working memory); and 3) to determine if TMS measurement (SICI) in children with NF1 will correlate with clinical effects of NAC treatment and evaluate utility of advanced brain imaging and spectroscopy measurements in children with NF1, and effects of NAC therapy.

We propose to study 58 children with NF1, ages 8-16 years, at baseline and after completion of 8 weeks of treatment with NAC, followed by a washout period of 4 weeks.

We believe this work has the potential to lay groundwork for future use of relevant biomarkers for treatment and outcomes research for NF1 as well as other biologically similar conditions, collectively designated the “RASopathies” (due to involvement of the RAS family of proteins) and ultimately to guide development of more effective treatments based on disease pathophysiology.

**STUDY OBJECTIVE:**

**NAC Trial at Cincinnati Children's Hospital Medical Center (CCHMC)**

We propose performing a single center randomized double-blind placebo controlled, prospective, Phase II study to explore safety, tolerability, and efficacy of NAC on motor behavior in children with NF1 aged 8 through 16 years old.

**Hypothesis:**

*We hypothesize that NAC therapy will improve motor function evaluated by the PANESS scale. This is based on studies demonstrating that NAC significantly improved impairments in the animal model of NF1. We will also analyze NAC effects on attention deficit and impulsivity in children with NF1.*

**Specific Aim:**

The primary outcome of this study is to characterize the effects of NAC treatment on motor function in children and adolescents with NF1 using the PANESS. We hypothesize that motor function scores rated with the PANESS scale will improve after treatment with NAC.

**Secondary Aims:**

1. To evaluate the effects of NAC on measures of NF1 neurocognitive symptomatology (ADHD/impulsive symptoms, executive function, working memory), we will use Response Evaluation in Neurofibromatosis and Schwannomatosis (REiNS) committee recommended assessments tools DuPaul ADHD rating scale (ADHD-RS), Behavioral Rating Inventory of Executive Function second edition (BRIEF-2), Wechsler Intelligence Scale for Children, Fifth Edition (WISC-V) subtests, and Test of Variables of Attention (TOVA).
2. To determine if TMS measurement (SICI) in children with NF1 will correlate with clinical effects of NAC treatment.
3. To quantify microstructural properties of brain tissue based on water diffusion, glutathione GSH concentrations, and  $\gamma$ -aminobutyric acid (GABA) concentration using brain magnetic resonance imaging (MRI) and magnetic resonance spectroscopy (MRS) in children with NF1. This will allow for regional correlation between imaging, spectroscopy and neuropsychometric outcomes. We will also determine if these magnetic resonance-based outcomes correlate with clinical effects of NAC treatment.
4. To evaluate safety and tolerability of NAC in children with NF1.
5. To explore motor function (PANESS) and brain-based measures (TMS, MRI-MRS, MRI-DTI) as biomarkers of impaired executive function (ADHD-RS; BRIEF-2; TOVA) in individuals with NF1.

**BACKGROUND:**

***Neurofibromatosis type 1 (NF1)***

Neurofibromatosis (NF1) is an autosomal dominant condition affecting many organs, resulting from mutations in the neurofibromin 1 gene [1]. Characteristically, individuals with this condition have cutaneous manifestations, most prominently hyperpigmented macules termed “café-au-lait” spots. The neurofibromin gene functions in part as a tumor suppressor, and persons with NF1 are susceptible to malignant and benign tumors in multiple organs. What is less well studied is that individuals with NF1 commonly suffer from difficulties with behavioral and emotional regulation including attention-deficit/hyperactivity disorder (ADHD) symptoms, learning disabilities, and developmental delays in motor function [2]. These cause substantial morbidity in childhood and throughout life. There are no effective treatments for motor behavior and/or learning difficulties for NF1 and other RASopathies. Lack of sensitive objective biomarkers that can evaluate motor system or behavioral symptoms causes difficulties in evaluating the efficacy of pharmacological interventions in NF1.

*Preliminary results regarding motor function and brain-based measures as a rationale for additional study.* A pre-planned analysis of predictor variables for NAC response has been performed, prior to breaking the blind in the randomized controlled treatment study. We performed these analyses on measures obtained at the baseline (pre-treatment) visit. These findings are now published, and some additional findings will be presented at scientific meetings. The strength of these preliminary findings warrants an expansion of the secondary aims, in order to validate these measures in a larger sample. Inclusion/exclusion criteria will be minimally changed to expand eligibility without compromising safety or study rigor. Individuals not wishing to participate in the NAC vs. Placebo treatment may elect to enroll and participate in an assessment of the baseline biomarkers. This will allow for additional assessment of the relationship between these measures and the NF1 diagnosis as well as for associations with motor and cognitive/behavioral impairments.

### **STUDY DESIGN:**

This is a prospective single-center; randomized, double-blind, placebo-controlled Phase II study to determine the safety and efficacy of NAC on motor behavior and/or attention deficits of children with NF1 aged 8 to 16 years. Participants will be randomized to 8-weeks of treatment with NAC (70 mg/kg/day) versus placebo. This is a collaborative study between multiple specialties at CCHMC and external collaborators at Children’s National Hospital and Technion Israel Institute of Technology. We have received IND approval from the FDA to use NAC for the application in this study (IND# 139468).

It is plausible and ethical to employ a placebo group, as no standard therapy with established efficacy is being withheld. There is no crossover in this study due to a lack of data concerning the length of possible washout effects. Primary and secondary outcome measures will be administered at baseline, after 8 weeks of treatment and at follow-up, 4 weeks after cessation of treatment to determine any washout effects.

In addition, the effect of NAC on measures of impulsivity, attention, executive function, and SICI and imaging biomarkers will be assessed. Participants will be carefully monitored for side effects by a medical safety monitor for the study. The safety of NAC will be evaluated using laboratory tests, clinical signs and adverse effects, which will be monitored at regular intervals over the 8-week treatment period.

An additional cohort of age/sex-matched NF1 participants will be recruited in order to characterize and validate biomarkers of brain function.

**DURATION:**

The current plan is for the study to last for 4 years. Data analysis and completion of study reports/papers will occur in the last 6 months of the study.

**SELECTION AND RECRUITMENT OF PARTICIPANTS:**

We plan to enroll 58 children ages 8-16 years with NF1 (**Figure 16**). Recruitment will be primarily from the NF1 and RASopathies Programs at CCHMC. The multidisciplinary program at CCHMC follows over 1500 individuals with NF1 and over 60% are under 20 years of age. We will also recruit from local events (including philanthropic and education events). Advertisements may also be posted on the NF1-associated websites including, but not limited to the Children's Tumor Foundation (CTF) website, NF1 facebook group, RASopathy facebook group, et cetera. Physical presence of research personnel in the clinic has been minimized in response to the covid-19 pandemic. Video recordings may aide recruitment and explanation of study assessments/details. These recordings may be distributed in a similar manner to other advertisements (NF1-associated websites, philanthropic/educational events, through interactions related to clinic visits, et cetera). Examples or video content would be a short description of TMS and PANESS procedures. A general outline of the study (risks/benefits, procedures, timeline, et cetera) as would be described during informed consent would also be advantageous.

An additional “Single visit, non-treatment” cohort will be recruited of 40 individuals with NF1 for a single “biomarker” study visit. These individuals will undergo motor function (PANESS) and brain-based measures (TMS, MRI-MRS, MRI-DTI) as biomarkers of impaired executive function (ADHD-RS; BRIEF-2; TOVA), but will not be assigned to receive NAC/Placebo.

We will use control data from age matched children ages 8-16 years, from previous studies (cohorts of 52 children with ADHD and 62 typically developing children).

We will also use advertising materials approved through the CCHMC Institutional Review Board (IRB). These include emails and small flyers which are posted at CCHMC locations. The study will be posted in clinicaltrials.gov.

**Inclusion criteria :**

1. Male and females aged 8 - 16 years (up to 16 years and 6 months) at time of enrollment
2. Meets NIH diagnostic criteria for NF1
3. Abnormal PANESS study (score at or above the age/sex-based mean)
4. Participants must have a full-scale intelligence quotient (IQ) of 70 or above, as determined by neurocognitive testing within the last 3 years or during the enrollment process
5. Participants on stimulant or any other psychotropic medication should stay on a stable dose (no change in dose) for at least 30 days before entering the study. A stable dose should be maintained throughout the study until completion of all study visits.

**Exclusion criteria:**

1. Participants should not be receiving chemotherapy currently, or have received chemotherapy in the 6 months prior to entering the study
2. Active intracranial lesions (stable low-grade glioma is acceptable) ψ
3. History of seizure disorder or epilepsy. History of a single seizure that occurred more than 12 months prior to enrollment is acceptable. History of febrile seizures if the last febrile seizure occurred more than 12 months prior to enrollment is acceptable. Recurrent, unprovoked seizures (epilepsy) is sufficient for exclusion. ψ
4. Major Depression, Bipolar Disorder, Conduct Disorder, Adjustment Disorder, other major Anxiety Disorders, or other developmental psychiatric diagnoses, based on history
5. For females, pregnancy
6. Implanted brain stimulator, vagal nerve stimulator, ventriculoperitoneal shunt, cardiac pacemaker, or implanted medication port ψ
7. Asthma (bronchospasm has been reported as occurring infrequently and unpredictably when NAC is used as a mucolytic agent)
8. High risk of upper gastrointestinal hemorrhage. Examples: presence of esophageal varices or peptic ulcers
9. Current use of MEKINIST (MEK-inhibitor) or use within 30 days

ψ Indicates Inclusion/Exclusion Criteria for the treatment- and non-treatment cohort (no mark indicates exclusion requirements for the treatment-cohort only).

**Inclusion of women and minorities:** We will include males and females in numbers consistent with the distribution expected in the clinic populations. We will not exclude any participant based on race or ethnicity.

[figure not shown]

Figure 16: NAC phase II double-blind placebo controlled study design.

of randomization, each participant will be assigned a unique medication kit identification number that will be used throughout the duration of the study.

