**POTENTIAL RISKS, DISCOMFORTS, INCONVENIENCES AND PRECAUTIONS:**

**Known and potential discomforts or hazards of single and paired pulse TMS:**

Single and paired pulse TMS has been used at CCHMC under [name] direction since 2001 for research only. Potential discomforts are mild and transient. In a prior study of 40 healthy and ADHD children, Garvey et al asked children to rank TMS compared to other childhood activities. TMS was ranked preferable to 1) a "shot"; 2) going to the dentist; and 3) a long car ride. The following mild, transient effects were reported in our prior study of 35 children and adults: scalp discomfort (12%), hand weakness (9%), headache, neck pain, arm pain, and arm tingling (6%), hand pain, decreased hand dexterity, hearing changes, and tiredness (3%). All of these had resolved by the following day. There were no physical findings after TMS supporting the subjective descriptions of loss of strength or dexterity. A prior common concern about use of TMS was the risk of seizures [28]. We follow recommended guidelines [28] and have seen no seizures in children or adults studied at our center. In addition, more recent studies even in children with epilepsy suggest that the risk of TMS inducing seizures is extremely low.

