**Known and potential discomforts or hazards of MRI/MRS:**

There are no known risks injury associated with a brain MRI/MRS. A few common less serious risks have been reported and are described here. Participants susceptible to claustrophobia may experience anxiety during the scan. The noise generated by the MRI/MRS machine can be

uncomfortable for some participants. Ear protection will be available to minimize the noise exposure. Participants may experience mild muscle/nerve stimulation that may feel like a twitching sensation.

Participants with a medical implant or external accessory device may experience complications with that device while undergoing an MRI/MRS. One potential complication is that the device may move in response to the magnet. Implants, external and accessory devices may heat up in response to the magnet, which could lead to burns. A third potential complication is the potential that electrochromic implants, external and accessory devices may malfunction in response to the magnet. To mitigate the risk of harm, we have included the use of such implants/devices as an exclusion factor for this study.

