#### **Precautions, risk minimization:**

The protocols include a number of precautions to minimize risk. Standard of care will be followed for all procedures performed to decrease the risk of infection, pain, bleeding, and bruising. The TMS laboratory was established in 2001 in consultation with [name], an internationally known researcher in transcranial magnetic stimulation. A trained and TMS-administration certified neurologist will be present during TMS. All subjects will wear 34 NRR earplugs or headphones during TMS if the head is stimulated at an intensity of over 90%. Standard exclusion criteria are applied for participation in this study. Detailed questioning for any adverse events will occur after the experiment and the next day after the study. Access to the Magstim Stimulator is Limited – these TMS devices are kept in room 4 of the EEG lab on the seventh floor of the A tower. The laboratory is continually monitored by CCHMC during business hours and is locked at all other times.

The effects the study drug and procedures would have on a fetus are unknown. When deemed appropriate by the study doctor or designee, pregnancy testing will be utilized before study procedures will take place. Females that test positive for pregnancy will be excluded or withdrawn from the study. Risks to a fetus conceived while on study drug will be reviewed with all parents. A conversation about risks and the importance of contraception while in this study will also be conducted with participants when deemed appropriate by the study doctor or designee. Consent to participate in this study includes promise of compliance with appropriate contraceptive measures. Females will use an effective means of birth control (i.e. abstinence, hormonal, or intrauterine device) during the study and for 30 days after taking the last dose of study drug. Males will use an effective means of birth control (i.e. abstinence or double-barrier contraception) during the study and for 90 days (3 months) after taking the last dose of study drug.

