During screening, children will receive a review of systems and physical examination, laboratory measures (CBC, basic chemistries with liver transaminase, thyroid function test, urinalysis), and pregnancy test (if relevant). Pregnancy tests will be administered when deemed appropriate by the study doctor or designee. Results of the pregnancy test will be provided to the parent/guardian of the participant. If an uninterpretable urine pregnancy test is obtained or if the participant cannot/refuses to provide a urine sample, then a serum pregnancy test will be performed. All values outside the reference range will be assessed by the investigator, [name], for clinical relevance.

All MRI's will undergo a safety review by a radiologist in order to determine whether there are any clinically relevant incidental findings that require referral for appropriate clinical follow-up. Referrals for clinical follow-up will be provided and that an individual with appropriate clinical qualifications will inform the research subjects of the need for the clinical follow-up.

Measurement and Management of Adverse Effects:

Participants and parents/guardians will be given the opportunity to report AEs to the investigator spontaneously in response to a general prompt (e.g. "Any changes in your health since the last visit?"). Terminology for adverse events (AEs) will follow the Medical Dictionary for Regulatory Activities (MedDRA) version 20.1 (<https://www.meddra.org>) (Table 6). If AEs occur, the investigator will rate the seriousness of the event, whether the event was anticipated, and the likelihood that it is related to NAC. Serious events will be reported to the IRB within 24 hours of awareness. All other adverse events will be reviewed quarterly by the study team.

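### Pregnancy exclusion and the scheduled pregnancy test are limited to the treatment cohort, although the single-visit cohort also has TMS and MRI and the precaution cites the procedures

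*Combined protocol and SAP*

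**What the plan says.** Exclusion 5 reads "For females, pregnancy" and has no ψ. The note under the exclusion list says that ψ marks criteria for both cohorts and that "no mark indicates exclusion requirements for the treatment-cohort only". Table 4 (Schedule of Assessments) uses the same symbol for procedures done in both cohorts. Its MRI/MRS and TMS rows carry the symbol; its urine pregnancy row, at Visits 1 and 2, does not.

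The section headed Precautions, risk minimization takes a wider view. It says: "The effects the study drug and procedures would have on a fetus are unknown". It continues: "When deemed appropriate by the study doctor or designee, pregnancy testing will be utilized before study procedures will take place". On a positive result: "Females that test positive for pregnancy will be excluded or withdrawn from the study". None of these three sentences is confined to one cohort. The medical and safety assessments under Compliance and Safety Monitoring repeat the discretion: "Pregnancy tests will be administered when deemed appropriate by the study doctor or designee".

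Selection and Recruitment of Participants plans 40 single-visit participants. That section and the one headed Non NAC/Placebo treatment cohort both say that this cohort has TMS and MRI but no study drug.

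**The concern.** The protocol gives its own reason for caution in pregnancy, and that reason includes the procedures. A cohort that has the procedures without the drug therefore falls within the reason but outside the eligibility rule. A girl known to be pregnant could meet every listed criterion for the single visit and go on to TMS and MRI. A girl not known to be pregnant would have no scheduled test.

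What is at stake is the consistent application of a safety rule in minors. The point has no bearing on sample size, type I error or the treatment effect estimate. It also needs no claim that TMS or MRI harms a fetus: the protocol says only that the effects are unknown.

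**Working it through.** No calculation applies. The check sets the relevant places side by side.

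1. **Exclusion list.** Of nine exclusions, three carry ψ: item 2 (active intracranial lesions), item 3 (seizure disorder) and item 6 (implants). Item 5, pregnancy, is one of the six that do not. By the note, it applies to the treatment cohort only.

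2. **Table 4.** Brain imaging, TMS and the eligibility review are marked for both cohorts. The urine pregnancy row is not, and nor are vitals, safety labs and physical exam. The single-visit cohort is thus scheduled for the procedures but not for the test.

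3. **Procedures in the single-visit cohort.** TMS and MRI, as stated in two sections and confirmed by the marks in Table 4.

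4. **Precaution.** Its opening sentence names drug and procedures together. Its testing sentence places the test ahead of study procedures, and its exclusion sentence refers to the study as a whole. Taken on their words, all three reach the single-visit cohort.

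5. **How far the precaution protects without the mark.** Exclusion under it follows a positive test. Testing is discretionary in both places where it is described, and is not scheduled for this cohort. The medical and safety assessments name no cohort either, but they list the pregnancy test alongside a physical examination and laboratory measures that Table 4 does not mark for single-visit participants. That text cannot be relied on to cover them.

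6. **Comparison with other procedure hazards.** On TMS, the risk section says: "A prior common concern about use of TMS was the risk of seizures". The matching exclusion, item 3, is marked. On MRI and implants it says: "To mitigate the risk of harm, we have included the use of such implants/devices as an exclusion factor for this study". The matching exclusion, item 6, is marked. Pregnancy is also tied to the procedures, in the precautions section, but is not marked.

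7. **Who could be affected.** Only pregnant females within the cohort of 40. Study Design says this cohort is matched on age and sex, and the trial's age range is 8 to 16 years. The documents give neither the number of females nor any pregnancy rate, so no count can be derived.

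**The case against.** The strongest reply is that the omission is intended. The exclusion list and Table 4 agree in leaving pregnancy unmarked, which looks more like a deliberate allocation than a slip on one line. The marked exclusions follow specific procedure hazards, so the authors may have judged that pregnancy was not one. The MRI/MRS risk text reports no known risk of injury, and the TMS text describes mild, transient discomforts. Most of the rest of the pregnancy paragraph concerns the drug: conception while taking it, and contraception for 30 or 90 days after the last dose. None of that fits a single visit without drug.

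This reading is plausible and cannot be ruled out. It does not settle the point, because the sentences that name the procedures are not limited to the treatment cohort, and the MRI/MRS risk text does not mention a fetus or cover TMS. If the omission is intended, the precautions section should say so.

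A second reply is that the precaution already protects everyone, since staff may apply the stricter rule without breaching the eligibility list. That is true, and other sections clearly supplement the marks: no inclusion criterion carries ψ, yet the single-visit participants must have NF1. But the protection depends on a discretionary test that this cohort's schedule does not contain. Screening also uses an eligibility checklist, which is not among the documents and may or may not close the gap.

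A reader might infer that the protocol contradicts itself outright, or that it means pregnant girls to be scanned. The documents do not support either. The two rules can both be followed, and nothing invites the enrolment of pregnant participants.

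**Conclusion.** The point holds as a minor inconsistency in safety text. The eligibility list and the schedule confine the pregnancy exclusion and the scheduled test to the treatment cohort, while the stated reason for the precaution covers procedures that both cohorts undergo. This rests on reading the precaution's words as they stand, without an unstated limit to the treatment cohort.

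The number affected is unknown and, given the age range, probably very small. A reader might take the cohort's share of planned NF1 participants, 40/(58 + 40) = 40/98 = 41%, as the size of the problem. It is not: that share includes boys and young children and says nothing about how many could be pregnant. None of the 58 randomized participants is affected, and the randomized comparison is unchanged.

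**What to change.** Add ψ to exclusion 5, so that pregnancy excludes in both cohorts. Add Ψ to the urine pregnancy row of Table 4 for the single visit, before TMS and MRI, with testing at the discretion of the study doctor or designee as the precautions and the medical and safety assessments already provide. Both marks are needed: marking exclusion 5 alone would leave the schedule out of step with the eligibility list.

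If the omission was intended, the alternative is a sentence limiting the precaution to the treatment cohort and giving the reason. Marking both places is preferable, because it follows the protocol's own stated caution.

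The cost is two marks in the protocol, an occasional urine test and a rare exclusion from the single-visit cohort. Sample size and analysis do not change.
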